5.2 SUBJECT EXCLUSION CRITERIA

Subject Exclusion Criteria: Subjects eligible for this study must not meet any of the following criteria:

1. Pelvic floor physical therapy within the last 6 months
2. History of pelvic radiation treatment
3. History of urethral diverticula
4. History of urethral sling, anterior prolapse repair, ureteral bulking agents and/or other SUI procedure or surgery
5. Known vesicoureteral reflux, vaginal prolapse beyond the introitus, or other significant pelvic floor abnormalities
6. Patient has urinary incontinence of neurogenic etiology
7. Patient is morbidly obese (defined as 100 pounds over their ideal body weight, or body mass index 40 or greater)
8. Chronic hepatitis
9. Hepatic cirrhosis
10. HIV and/or hepatitis A, B, or C

11. Subjects taking systemic hormone products (excludes intravaginal application of estradiol topical/tablet agents and hormones delivered via vaginal rings)
12. Subjects with a history of breast or endometrial cancer.
13. Subjects with cerebrovascular disease, thromboembolic disorders, myocardial infarction, or angina.
14. Subject with an entry measurement of > 5 mm endometrial stripe thickness as measured by MRI.
15. Any other condition which per investigators' judgement may increase subject risk
16. Clinically confirmed urinary tract infection

5.3 STRATEGIES FOR RECRUITMENT, RETENTION, AND TO IMPROVE ADHERENCE TO INTERVENTION PROTOCOLS

Potential subjects will be identified from existing medical records, physician referrals, or recruited via advertisement or word of mouth. During initial telephone contact, patients' history will be reviewed for inclusion/exclusion criteria. Those subjects who initially qualify will be invited to an in person study visit (study visit 1).

5.4 TREATMENT ASSIGNMENT PROCEDURES

All subjects enrolled in this study will receive a daily oral dose of GTx-024, 3 mg.

5.4.1 REASONS FOR WITHDRAWAL

Subjects are free to withdraw from the study at any time for any reason.

In addition, subjects may be withdrawn from the study by the Principal Investigator (PI) in consultation with GTx, Inc. for reasons potentially including:

- Unable to tolerate study treatment (AE requiring permanent discontinuation of study treatment)
- AEs that require treatment with a prohibited medication or a procedure
- Development of any condition that may pose an additional risk to the subject or PI decision that this is in the best interest of the subject
- Study terminated by sponsor
- Subject unable to follow Investigators' instructions and comply with the study procedures
- Major protocol violation

The clinical study report will include reasons for all subject withdrawals from treatment and from the study as well as details relevant to violations of Study Prohibitions and Concomitant Therapy.

5.4.2 EARLY TERMINATION OR SUSPENSION OF THE STUDY

Any decision to suspend enrollment or terminate the study will be made by the Sponsor, PI and, if appropriate, the local IRB. If a decision is made to terminate the study, subjects who have received treatment will be followed for up to 28 days.

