Statistical Considerations:	
This is a proof of concept feasibility study, so no power calculation is needed. Therefore, up to 35 subjects meeting inclusion/exclusion criteria will be recruited until 30 subjects have completed treatment. Descriptive statistics will be performed to explore changes in primary and secondary outcomes measures between baseline and end of treatment. The primary efficacy measure will be a reduction in the number of stress incontinence episodes/day. Secondary efficacy measures will include reduction in number of voids per day, volume of voids, 24 hour pad weight, responses to validated questionnaires, changes in UPP measures, changes in sexual function, and changes in pelvic floor muscles as measured by MRI.
 
Safety will be determined by the number and type of adverse events reported during treatment. Various imputation methods may be explored.

Study Intervention/Treatment:	
Participation in this study includes 5 in person study visits and two telephone and/or mailed questionnaire visits. Additional in person and/or telephone visits may be added as needed.
 
Study subjects will receive 3 mg of GTx-024 orally daily.

Table 1. Schedule of Measures.

	Screening Visit Days -21-0	Additional Screening Days -21-0	Visit 1. Baseline³ Week 0	Visit 2. Week 1 ± 3 days	Visit 3. Week 4 ± 3 days	Visit 4. Week 8 ± 3 days	Visit 5. Week 12 ± 3 days	Visit 6. Week 16 ± 7 days
	Clinic Visit	Clinic Visit	Clinic Visit	Phone Call	Clinic Visit	Clinic Visit	Clinic Visit	Phone Call and Mail
Consent	x							
Inclusion/Exclusion	x		x					
History			x					
Interview/Vital Signs	x		x		x	x	x	
Height/Weight	x				x	x	x	
24 hour Pad Weight	Instruct		x		x	x	x	
3 day Voiding Diary	Instruct		x		x	x	x	
Serum AST, ALT, Total Bilirubin	x				x	x	x	
Serum FSH ¹ ,	x							
CBC			x				x	
UA Dipstick (with culture as needed)	x		x				x	
Lipid Panel			x				x	
Testosterone Levels			x				x	
SHBG			x				x	
UPP			x				x	
Pelvic MRI		x					x	
Bladder Stress Test	x						x	
Mammogram ²		x						
Begin Daily ⁴ Treatment			x					
End Treatment							x	
Concomitant Meds	x		x	x	x	x	x	x
Adverse Events			x	x	x	x	x	x
HIV, Hep A, B, C Testing	x							
UDI-6; IIQ			x		x	x	x	x
PGI-S			x		x	x	x	x
MESA Questionnaire	x				x	x	x	x
PGI-I					x	x	x	x
FSFI Questionnaire			x		x	x	x	x
Bladder Scan PVR			x		x	x	x	
Ciprofloxacin 500 mg po (or equivalent)			x				x	
Focused Physical Exam			x				x	

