2.2 RISKS ANALYSIS AND RISK ASSESSMENT

2.2.1 POTENTIAL ANTICIPATED ADVERSE EVENTS

An adverse event is any clinical event that impacts, or that has the potential to impact, the health or safety of a Clinical Study subject caused by or associated with the study device and/or testing. Assessment for potential adverse events will be ongoing throughout this trial.

The benefits of treatment may include improvement in the frequency, or severity of urine loss, and improvement in quality of life. Decreases in serum triglycerides, cholesterol, and body fat, and improvements in insulin resistance, lean body mass and physical endurance are also possible benefits.

Adverse event tables and serious adverse events discussed below and are presented separately by adverse events reported among healthy volunteers on a single trial of 86 days of GTx-024 3 mg versus placebo and those enrolled on cancer trials of at least 86 days exposure to GTx-024 3 mg or placebo.

Adverse events reported among > 5% of GTx-024 3mg treated healthy subjects
Percentage of subjects reporting a given adverse event at least once

Primary System Organ Class	Preferred Term	GTx-024 N=24	Placebo N=24
Gastrointestinal disorders	Diarrhea	8.3	12.5
	Dyspepsia	8.3	8.3
	Vomiting	8.3	0.0
General disorders and administration site conditions	Vessel puncture site bruise	12.5	4.2
	Fatigue	8.3	8.3
	Malaise	8.3	0.0
Infections and infestations	Herpes simplex	8.3	0.0
Injury, poisoning and procedural complications	Contusion	8.3	4.2
Investigations	Alanine aminotransferase increased	20.8	0.0
Musculoskeletal and connective tissue disorders	Back pain	12.5	16.7

Primary System Organ Class	Preferred Term	GTx-024 N=24	Placebo N=24
Nervous system disorders	Headache	20.8	20.8
	Dizziness	12.5	4.2
Respiratory, thoracic and mediastinal disorders	Pharyngolaryngeal pain	12.5	12.5

No serious adverse events (SAEs) were reported on this trial.

These side effects are based on information obtained from a clinical study (G200501) administering GTx- 024 3 mg for 86 days in healthy subjects– elderly males and postmenopausal females. Studies suggest that side effects associated with the study drug resolve after GTx-024 is stopped.

**Adverse events reported among > 5% of GTx-024 3 mg treated cancer subjects
Percentage of subjects reporting a given adverse event at least once**

Primary System Organ Class	Preferred Term	GTx-024 N=432	Placebo N=378
Blood and lymphatic system disorders	Anemia	34.7	34.7
	Neutropenia	18.3	23.3

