	Thrombocytopenia	10.4	10.8
	Leukopenia	8.3	9.0
Gastrointestinal disorders	Nausea	34.7	34.9
	Vomiting	20.1	21.2
	Constipation	12.3	10.1
	Diarrhea	11.6	12.7
General disorders and administration site conditions	Abdominal pain	5.1	3.7
	Fatigue	15.7	16.7
	Asthenia	15.3	13.5
	Disease progression	11.8	16.7
Infections and infestations	Pyrexia	10.2	9.8
	Pneumonia	5.6	7.1
Investigations	Blood creatinine increased	8.1	5.0

Primary System Organ Class	Preferred Term	GTx-024 N=432	Placebo N=378
	Weight decreased	6.0	4.8
Metabolism and nutrition disorders	Decreased appetite	10.6	14.8
Musculoskeletal and connective tissue disorders	Arthralgia	8.1	7.9
	Pain in extremity	5.6	4.2
Nervous system disorders	Headache	7.4	6.1
	Peripheral sensory neuropathy	5.8	3.4
	Dizziness	5.6	6.3
Respiratory, thoracic and mediastinal disorders	Dyspnoea	12.3	7.4
	Cough	9.5	9.3
Skin and subcutaneous tissue disorders	Alopecia	17.8	18.5

Serious adverse events (SAEs) reported among > 2% of GTx-024 3 mg treated cancer subjects

Percentage of subjects reporting a given serious adverse event at least once

Primary System Organ Class	Preferred Term	GTx-024 N=432	Placebo N=378
Blood and lymphatic system disorders	Anemia	4.2	3.7
	Neutropenia	3.2	3.7
	Febrile neutropenia	2.3	1.6
Blood and lymphatic system disorders	Thrombocytopenia	2.3	1.6
General disorders and administration site conditions	Disease progression	7.9	11.9
Infections and infestations	Pneumonia	3.5	3.2
Neoplasms benign, malignant and unspecified (incl cysts and	Malignant neoplasm progression	2.8	2.1

An AE that appears related to GTx-024 in clinical trials has been a dose-dependent, transient, asymptomatic increase in ALT. However, these increases were modest at doses up to 10 mg per day. Most of the subjects studied to date had ALT levels that

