2.2.3 METHODS TO MINIMIZE RISK

Subjects will be monitored at each visit for changes since last visit and adverse effects of treatment. Since elevations in ALT are possible, serum liver function tests will be monitored during treatment. (Refer to Section 9.4 Halting Rules)

Subjects will receive a prophylactic antibiotic at visits where catheterization/UPP occur to decrease risk of urinary tract infection (UTI). Any infection will be appropriately treated.

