concomitant meds and adverse events, including any vaginal bleeding, discharge, infections and/or spotting, will be assessed and recorded. Subjects will also be instructed to complete a 24 hour pad weight and 3 day voiding diary in the week preceding their next study visit. A 30 day supply of study drug will be dispensed with administration instructions.

Study Visit 4: Week 8, Clinic Visit

Approximately 8 weeks after beginning treatment, subjects will return to the clinical research office for an in person visit. An interview and vital signs will be conducted. Height and weight and PVR will be measured. Pad weights will be measured, and the 3 day voiding diary will be collected and reviewed. Blood will also be drawn to measure serum AST, ALT, and total bilirubin. Questionnaires will also be completed and concomitant meds and adverse events including any vaginal bleeding, discharge, infections and/or spotting, will be assessed and recorded. Subjects will also be instructed to complete a 24 hour pad weight and 3 day voiding diary in the week preceding their next study visit. A 30 day supply of study drug will be dispensed with administration instructions.

Study Visit 5: Week 12, Clinic Visit

Approximately 12 weeks after beginning treatment, subjects will return to the clinical research office for an in person visit. An interview with vital signs will be conducted. A focused physical exam will be done. Gynecological pelvic exam will only be done at this visit if clinically indicated. Urine dipstick will be done and PVR will be measured. Height and weight will be measured. 24 hour pad weights and 3 day voiding diaries will be collected/reviewed. Blood will also be drawn to measure laboratory values as outlined in Table 1. UPP, Bladder Stress Test, and MRI will be performed at end of treatment, questionnaires will be administered, and concomitant medications/adverse events will be assessed and recorded. All study medication will be collected and accounted for.

Study Visit 6: Week 16, Telephone/mailed questionnaire visit

Approximately 4 weeks after study drug treatment has ended, subjects will be contacted by phone to assess for concomitant meds and adverse events. Subjects will also be instructed to complete and return mailed questionnaires.

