7.2 EARLY TERMINATION

Subjects may withdraw from the study voluntarily. In addition, if the PI determines that continued participation might present a safety risk for the subject then the PI may withdraw the subject from the study. Those subjects who receive study drug will be followed for 28 days after stopping study participation. Every effort will be made to obtain all end of treatment measures as outlined in (Table 1.Visit 6) in the event that a subject withdraws, or is withdrawn, from the study before completing treatment.

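### Section 7.2 sends women who stop early to Visit 6, a phone and mail contact; the end-of-treatment measures, including AST, ALT and bilirubin, are at Visit 5.

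*Combined protocol and SAP*

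**What the plan says.** Section 7.2 is the only text that lists measures for a woman who stops before completing treatment. It reads "Every effort will be made to obtain all end of treatment measures as outlined in (Table 1.Visit 6"), and it also asks for 28 days of follow-up.

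Visit 6 in Table 1 is the Week 16 contact by phone and mail. Section 7.1 describes it as a call about concomitant medications and adverse events, after which "Subjects will also be instructed to complete and return mailed questionnaires". The visit that Table 1 marks as the end of treatment is Visit 5, Week 12.

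The Table 1 row "Serum AST, ALT, Total Bilirubin" is marked at Screening and at Visits 3, 4 and 5. It is blank at Visit 6.

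For termination of the whole study, Section 5.4.2 says "If a decision is made to terminate the study, subjects who have received treatment will be followed for up to 28 days" and names no assessments. Section 5.4.1 includes "Study terminated by sponsor" among the reasons for withdrawing a subject, so the early-stop rule in 7.2 applies to termination as well.

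On liver safety, Section 2.2.1 says that an event apparently related to the drug is a "dose-dependent, transient, asymptomatic increase in ALT". Section 2.2.3 commits that "serum liver function tests will be monitored during treatment".

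**The concern.** The sentence in 7.2 contradicts itself. Its words ask for the end-of-treatment measures, but its reference leads to a column that has almost none of them. A coordinator who opens Table 1 at Visit 6 finds a phone call and five questionnaire rows, and draws no blood.

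Two things are lost. The first is a liver test at stopping. The drug's known laboratory effect causes no symptoms, so a phone interview cannot be expected to find it. A rise that is not measured is not recorded as an adverse event, is not followed under Sections 9.3 or 9.4, and is absent from the safety results, which Section 10 bases on the number and type of adverse events. A woman who stops before Week 4 could leave with no liver test on drug at all.

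The second is the efficacy data. The voiding diary behind the primary endpoint is not collected at Visit 6, nor is the pad weight. The urethral pressure profile, bladder stress test and MRI are scheduled only before treatment and at Week 12, so an early stopper handled by the cited column has no post-treatment value for any of them.

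**Working it through.** The plan gives no figure to reproduce on this point. The check is a comparison of two columns of Table 1, followed by simple arithmetic for size.

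**Step 1: Visit 5 against Visit 6 in Table 1**

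| Measure | Visit 5 (Week 12, clinic) | Visit 6 (Week 16, phone and mail) |
|---|---|---|
| AST, ALT, total bilirubin | yes | no |
| CBC, lipid panel, testosterone, SHBG | yes | no |
| 3-day voiding diary | yes | no |
| 24-hour pad weight | yes | no |
| Urethral pressure profile, bladder stress test, MRI | yes | no |
| Post-void residual, physical exam, vital signs | yes | no |
| UDI-6/IIQ, PGI-S, PGI-I, MESA, FSFI | yes | yes |
| Concomitant medications, adverse events | yes | yes |

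Everything at Visit 6 is also at Visit 5, so pointing 7.2 to Visit 5 loses nothing.

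**Step 2: does another section order a liver test at stopping?**

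- Section 2.2.3 commits to liver tests during treatment, on the Table 1 schedule.
- Section 9.3 follows adverse events to an outcome. It acts on events already known.
- Section 9.4 follows discontinued subjects until abnormal values normalise. It acts on values already found abnormal.
- Section 5.4.2 names no test.

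None does.

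**Step 3: number of early stoppers**

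Inputs: up to 35 subjects and 10-20% expected withdrawal (Section 10).

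35 × 0.10 = 3.5 and 35 × 0.20 = 7.

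**Step 4: how many of them would have an ALT rise at some point**

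Higher rate. In the healthy-subject table of Section 2.2.1, the row "Alanine aminotransferase increased" shows 20.8% of 24 on 3 mg and 0.0% of 24 on placebo over 86 days; 20.8% of 24 is 5.

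- 3.5 × 5/24 = 0.73 and 7 × 5/24 = 1.46.
- The exact (Clopper-Pearson) 95% interval for 5/24 is 7.1% to 42.2%, which gives 3.5 × 0.0713 = 0.25 up to 7 × 0.4215 = 2.95.

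Lower rate. The table for 432 treated cancer subjects lists events reported in more than 5%, and ALT increase is not in it. Unless a row was lost in text extraction, the rate there was at most 5%.

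- 3.5 × 0.05 = 0.18 and 7 × 0.05 = 0.35.

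These are upper figures for the harm. They count a rise at any time, not an undetected one; the 5/24 rate covers 86 days, while early stoppers have less exposure; and the Week 4 and Week 8 tests would find some rises. The documents do not allow an estimate of undetected rises.

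**The case against.** The strongest reply is that this is a slip in a visit number, not a gap in the design. The operative words in 7.2 are end-of-treatment measures, which fit only Week 12. The protocol also carries traces of a numbering that counts screening as Visit 1: Sections 5.3 and 6.8 label the first in-person or screening visit that way, and Section 4.1 has treatment starting at Visit 2. Counting on, Week 12 becomes Visit 6. A careful site might therefore draw the Week 12 bloods anyway. This explanation is plausible, and it indicates which visit was meant. It does not remove the error: in the current Table 1, Visit 6 is the phone contact, and collection at stopping should not depend on a site noticing the mismatch.

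Safeguards exist. Section 9.4 asks for every discontinuation to be discussed beforehand with the Medical Monitor, and the protocol summary allows extra visits as needed. Either could prompt a blood test; neither requires one.

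The clinical stakes are also limited. In these women dosing has already stopped. Section 2.2.1 reports that the rises were modest, that levels returned to normal when dosing was not continued, and that bilirubin did not rise significantly. This stands, and it sets the weight of the point.

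A reader might go further and infer that 5.4.2 is itself defective, or that termination cancels the safety follow-up in Section 9. The documents do not support either. Termination is a withdrawal reason in 5.4.1, so a corrected 7.2 covers it, and nothing says that Section 9 ceases to apply.

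**Conclusion.** The reference in 7.2 is wrong as written and should be corrected. Followed literally, it yields no liver test and none of the clinic end-of-treatment measures for women who stop early. About 3.5 to 7 of 35 women are affected at the planned withdrawal rate. As an upper figure, about 0.7 to 1.5 of them would have an ALT rise at some point if 5/24 applies, or about 0.2 to 0.35 at a 5% rate. The main consequence is incomplete capture of a known safety signal, with loss of efficacy data second. Serious harm to individual women is not the expected result.

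The size rests on three assumptions: the planned withdrawal rate holds, a rate from a different population carries over, and sites follow the cited column rather than the words before it.

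Two larger readings are tempting. One applies the ALT rate to all 35 women on drug at a termination. That does not fit six months of enrolment with 12 weeks of treatment: with even accrual (an assumption), about 35 × 12/26 = 16 are on drug at once. The other blames this error for the roughly four-week gaps between liver tests. Those gaps are the ordinary schedule for every participant, including completers.

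The plan does not say whether early-stop measurements would enter the Week 12 summaries, so no claim is made about bias in the primary analysis.

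**What to change.** In Section 7.2, change the visit number in the reference to Table 1 from 6 to 5. Keep the best-efforts wording and leave the 28-day follow-up sentence as it is. Because 5.4.1 treats termination by the sponsor as a withdrawal, this also covers early termination of the study. Section 5.4.2 needs at most a cross-reference to 7.2.

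The cost is one clinic visit with a blood draw per early stopper, about 3.5 to 7 women at the planned withdrawal rate, and more if the study is terminated while women are on treatment. The remaining Visit 5 procedures stay on a best-efforts basis. No endpoint, sample size or analysis changes.

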6. STUDY INTERVENTION/INVESTIGATIONAL PRODUCT

6.1 STUDY PRODUCT DESCRIPTION

GTx-024 (enobosarm); United States Adopted Names Council official generic name) is an orally bioavailable nonsteroidal SARM with tissue-selective anabolic and androgenic pharmacologic activity (Dalton, 2011).

6.2 ACQUISITION

GTx-024 3 mg Softgels (capsules) will be supplied by GTx, Inc.

6.3 FORMULATION, PACKAGING, AND LABELLING

The drug product will be supplied as opaque, white to off-white, size 5, oval Softgel capsules containing 3 mg GTx-024. "GTx" will be imprinted in black ink on the outer shell of the capsule. The liquid Softgel fill is composed of GTx-024 dissolved in polyethylene glycol 400 (PEG400).

GTx-024 3 mg Softgels will be packaged in high density polyethylene (HDPE) bottles with induction seal and child-resistant closure. Each bottle will contain sufficient study drug for 35 days of dosing according to the study protocol. Each bottle of study drug will be labeled with dosing and storage instructions.

6.4 PRODUCT STORAGE AND STABILITY

Recommended storage will be at controlled room temperature 15°C–25°C (59°F–77°F), with excursions permitted to 30°C (86°F), protected from moisture.

6.5 DOSAGE, PREPARATION, AND ADMINISTRATION OF STUDY INTERVENTION/INVESTIGATIONAL PRODUCT

One (1) GTx-024 3 mg Softgel capsule will be taken PO with water at approximately the same time each day, with or without food.

6.6 ACCOUNTABILITY PROCEDURES FOR THE STUDY INVESTIGATIONAL PRODUCT(S)

The Investigator is responsible for the correct storage of study medication according to GTx, Inc. recommendations. The study medication made available for this clinical trial must be used in accordance with the protocol and dispensed only under the supervision of the Investigator and documented sub-Investigators. The Investigator must maintain complete and accurate records, showing the receipt and disposition of all supplies of the study medication delivered by the GTx, Inc. authorized representative. These records must include a master record which lists the date of receipt of all study medication shipments, batch numbers, expiration date, and quantities received. In addition, a dispensing record which includes all quantities dispensed, identification of the subject to whom study medication was dispensed, the date of each dispensing, and the identification of the dispenser will also be maintained. The master dispensing records are separate from records kept for individual trial subjects.

It is the Investigator's responsibility to ensure that study medication used by trial subjects plus unused study medication equal the total amount received from the GTx, Inc. authorized representative. Damaged and/or contaminated packets must also be accounted for in the dispensing records. All discrepancies must be explained in writing. The study personnel responsible for study medication administration to the subject will record the date and time the initial treatment is given to the subject. In addition, the Drug Accountability case report form (CRF) will document any treatment interruptions or discontinuation.

